4. INVESTIGATIONAL PLAN

4.1. Overall Study Design

This is a Phase 2, open-label study designed to evaluate the safety and efficacy of 2 INCB050465 treatment regimens in subjects diagnosed with relapsed or refractory MZL (see [Figure 1](#)). A total of approximately 90 subjects will be enrolled.

Subjects with MZL that is relapsed or refractory to at least 1 line of prior systemic therapy that included an anti-CD20 antibody will be screened for eligibility. The study was originally planned to enroll 2 cohorts:

- Cohort 1: Subjects who have received prior ibrutinib (n = 60)
- Cohort 2: Subjects who have not received a prior BTK inhibitor (n = 60)

However, given the limited availability of ibrutinib (approved for MZL in the United States only), the number of subjects with relapsed or refractory MZL previously treated with ibrutinib is low. At the time of Protocol Amendment (Version) 3, only 2 subjects have been enrolled into Cohort 1, 18 months after the study start in JUN 2017. Therefore, Cohort 1 was closed to further enrollment for feasibility reasons.

Subjects already enrolled into Cohort 1 will continue to receive study treatment per the Protocol, and their data will be reported and analyzed separately from subjects in Cohort 2.

The first 60 subjects in Cohort 2 and any subjects enrolled in Cohort 1 who meet the eligibility criteria will be further allocated to 1 of 2 study treatment regimens through the IWRS (see [Section 5.1](#)):

- Treatment A: INCB050465 20 mg QD PO for 8 weeks followed by 20 mg once weekly PO.
 - Subjects in Cohort 1 receiving Treatment A will be referred to as Cohort 1A.
 - Subjects in Cohort 2 receiving Treatment A will be referred to as Cohort 2A.
- Treatment B: INCB050465 20 mg QD PO for 8 weeks followed by 2.5 mg QD PO.
 - Subjects in Cohort 1 receiving Treatment B will be referred to as Cohort 1B.
 - Subjects in Cohort 2 receiving Treatment B will be referred to as Cohort 2B.

To better understand the safety and efficacy of INCB050465, an additional 30 subjects will be enrolled into one of the two treatment regimens (A or B) being evaluated in this Study. The treatment regimen will be selected after enrollment is completed for Cohort 2 (ie, 60 subjects enrolled) and after evaluation of emerging safety and efficacy data from this and other

monotherapy studies of INCB050465 in NHL. Once a treatment regimen is selected, the non-selected treatment regimen will be closed to further enrollment. Subjects receiving the non-selected treatment regimen may switch to the selected treatment regimen or remain on their current treatment regimen, provided the subject has not met study-treatment withdrawal criteria and there are no safety concerns for their current treatment regimen. There will be no re-baselining for subjects who switch treatment regimens and all subjects will continue to follow the same assessment schedule.

NOTE: The primary, secondary, [REDACTED] objectives and endpoints described in Section 2 are applicable for both cohorts; however, the cohorts will be analyzed separately, when applicable, as detailed in Section 9.

[figure not shown]
Subjects will receive treatment until disease progression, death, unacceptable toxicity, or consent withdrawal.

Subjects will be monitored for safety and efficacy periodically until disease progression, death, unacceptable toxicity, or withdrawal of informed consent. An IDMC will review safety data periodically as stated in the IDMC charter. Subjects will be evaluated for ORR by an IRC and followed for DOR, PFS, and OS.

An interim futility analysis is planned for Cohort 2 when 30 subjects have been treated and have been evaluated for response or have permanently discontinued study treatment because of disease progression, withdrawal of consent, or death. Cohort 2 will be terminated for futility if ≤ 10 of the 30 subjects responded (ie, CR or PR) based on assessments provided by the IRC. A timely assessment of response will be performed to avoid the risk of overenrollment.

After treatment discontinuation, subjects will be followed for safety and survival. Subjects who have discontinued study treatment due to reasons other than disease progression will be followed for either radiologic disease progression, the start of a new anticancer therapy, or death, whichever comes first. It is expected that the final analysis will occur no later than 2 years after the first dose of INCB050465 is administered to the last subject treated.

Figure 1: Study Design of INCB 50465-204

BTKi = Bruton's tyrosine kinase inhibitor; EOT = end of treatment; MZL = marginal zone lymphoma; QD = once daily

^a A futility analysis will be performed for Cohort 2 when the first 30 patients have been treated and evaluated for response (see Section 9.6).

^b Subjects who discontinue study treatment for a reason other than disease progression will continue with disease assessments by radiologic imaging every 8, 12, or 24 weeks as appropriate with disease progression.

^c Every 12 weeks by clinic visit, telephone, or e-mail.

^d Urine pregnancy and dispensing of study treatment will occur every 4 weeks.

^e Per Protocol Amendment Version 3, Cohort 1 is closed to further enrollment

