Subjects already enrolled in Cohort 1 will continue to receive study treatment per the protocol, and their data will be reported and analyzed separately from subjects in Cohort 2.

Subjects in Cohort 2 (n = 60) will be further allocated to 1 of the 2 study treatment regimens as follows:

- Treatment A: INCB050465 20 mg once daily (QD) for 8 weeks followed by 20 mg once weekly.
- Treatment B: INCB050465 20 mg QD for 8 weeks followed by 2.5 mg QD.

Subjects will be evaluated for ORR by an IRC and for safety and will be followed for DOR, PFS, and OS. Subjects will receive treatment until disease progression, death, unacceptable toxicity, or consent withdrawal.

An interim futility analysis is planned when the first 30 subjects in Cohort 2 have been treated and evaluated for response or permanently discontinued study treatment because of disease progression, withdrawal of consent, or death. Cohort 2 will be terminated for futility if ≤ 10 of the 30 subjects have responded (ie, CR or PR) based on assessments provided by the IRC. A timely assessment of response will be performed to avoid the risk of overenrollment.

To better understand the safety and efficacy of INCB050465, an additional 30 subjects will be enrolled into one of the two treatment regimens (A or B) being evaluated in this Study. The treatment regimen will be selected after enrollment is completed for Cohort 2 (ie, 60 subjects enrolled) and after evaluation of emerging safety and efficacy data from this and other monotherapy studies of INCB050465 in NHL. Once a treatment regimen is selected, the non-selected treatment regimen will be closed to further enrollment. Subjects receiving the non-selected treatment regimen may switch to the selected treatment regimen or remain on their current treatment regimen, provided the subject has not met study-treatment withdrawal criteria and there are no safety concerns for their current treatment regimen. There will be no re-baselining for subjects who switch treatment regimens and all subjects will continue to follow the same assessment schedule.

Study Population: Subjects with histologically confirmed MZL, including extranodal, nodal, and splenic subtypes, who previously received 1 or more lines of systemic therapy, including at least 1 anti-CD20 antibody, with documented progression or documented failure to achieve CR or PR after the most recent systemic treatment regimen.

Key Inclusion Criteria:

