5. TREATMENT

5.1. Treatment Assignment

5.1.1. Subject Numbering and Treatment Assignment

Study sites will enter subject demographic and baseline data into the IWRS in order to receive a subject number and treatment allocation.

All subject numbers will be 6 digits; the first 3 digits will be the site number, and the last 3 digits will be the subject's number. This subject number will be maintained throughout the study and will not be reassigned. Subjects who withdraw consent or discontinue from the study after being assigned a subject number will retain their initial number.

Site staff will contact the IWRS to allocate the subject to treatment assignment and obtain the initial study treatment assignment. The investigator or designee will select the assigned bottles of study treatment from their stock that correspond to the number provided by the IWRS and dispense the study treatment to the subject. All subsequent dispensing of study treatment should follow this process. Refer to the IWRS Manual for detailed information.

If a subject is mistakenly given a bottle of study treatment that is not the bottle assigned by the IWRS, the IWRS help desk must be notified immediately. The reason for the misallocation of the study treatment must be documented by the study site and reported to the IRB/IEC.

For subjects who signed an ICF but are not allocated study treatment and for subjects who are allocated study treatment but were not treated, refer to the eCRF Completion Guidelines for instruction on which eCRFs to complete.

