5.1.2. Randomization and Blinding

Not applicable.

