An additional 30 participants will be enrolled into one of the two treatment regimens (A or B) being evaluated in this study to better understand the safety and efficacy of INCB050465. The treatment regimen will be selected after enrollment is completed for Cohort 2 (ie, 60 participants enrolled) and will be selected after evaluation of emerging safety and efficacy data from this and other monotherapy studies of INCB050465 in non-Hodgkin's lymphoma. Once a treatment regimen is selected, the non-selected treatment regimen will be closed to further enrollment. Participants receiving the non-selected treatment regimen may switch to the selected treatment regimen or remain on their current treatment regimen, provided the participant has not met study-treatment withdrawal criteria and there are no safety concerns for their current treatment regimen. There will be no re-baselining for participants who switch treatment regimens and all participants will continue to follow the same assessment schedule.

Participants will receive treatment until disease progression, death, unacceptable toxicity, or consent withdrawal. Participants will be evaluated for ORR by an IRC and followed for DOR, PFS, OS, and safety.

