### Amendment 1 (27 AUG 2020)

- Section 4.1.4 was updated to include details of rules for handling partial/missing onset or end date of TEAEs in the calculation of time to onset or duration of a TEAE. Rules for partial/missing date of last dose were updated to include details of handling situations where both month and day are missing.
- Section 5.2 was modified to provide details regarding how crossover participants will be summarized.
- Section 5.3 was updated to remove the efficacy evaluable analysis set and use the FAS for all analyses on efficacy data. This change is to comply with comments from FDA that any participants who received at least 1 dose should be included in the efficacy analyses for a single-arm trial. The all-screened population was added for the summary of analysis populations.
- Section 6.1.2 was modified to remove summaries of tumor markers but only keep listings. Relapsed/refractory status to the most recent prior therapy was added to the summary table of disease history because the response to last regimen before entering the study may be a prognostic factor for clinical outcomes.
- Section 6.2 was modified to add summaries of participants who are ongoing with treatment or still in the study.
- Section 6.4 was modified to change the calculations of duration of treatment and average dose during the maintenance dosing period because Group B with 2.5 mg QD was selected as the maintenance dose.
- Section 7.3 and Section 7.4 were modified to add efficacy analyses for participants in the FAS who have at least 2 prior therapies to support an indolent NHL indication in the same line of therapy as with follicular lymphoma in Study INCB 50465-203.
- Section 7.3.1 was modified to replace the efficacy evaluable analysis set with the FAS. This change is to align with Protocol Amendment 4 dated 23 DEC 2019 and include all treated participants in the efficacy analyses to comply with comments from FDA.
- Section 7.3.2 was modified to add "unknown" as a category for bone marrow involvement at baseline. Relapsed/refractory status to the most recent prior therapy was added to the subgroup analysis because the response to last regimen before entering the study may be a prognostic factor for clinical outcomes.
- Section 7.4.3 was modified to update references of censoring for PFS.

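### The first 60 Cohort 2 participants are split between Treatments A and B with no random or stated rule, yet their data help choose the regimen, so that choice and the by-regimen results (not the pooled ORR) can be confounded

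*Protocol*

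**What the plan says.** **Allocation.** The Protocol synopsis says Cohort 2 participants "will be further allocated to 1 of the 2 study treatment regimens as follows". Protocol 4.1 says the first 60 of them "will be further allocated to 1 of 2 study treatment regimens through the IWRS" and refers to Section 5.1. Section 5.1.1 says: "Study sites will enter subject demographic and baseline data into the IWRS in order to receive a subject number and treatment allocation". It does not say how those data, or anything else, determine the regimen. Section 5.1.2, headed "Randomization and Blinding", reads "Not applicable". SAP 3.1 says the same of randomisation.

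**Use of the data.** The synopsis says the regimen for 30 additional participants is chosen "after evaluation of emerging safety and efficacy data from this and other monotherapy studies of INCB050465 in NHL". SAP 3 repeats that it "will be selected after evaluation of emerging safety and efficacy data from this and other monotherapy studies of INCB050465". No criterion or weighting is given. The SAP change log for Amendment 1 (27 AUG 2020) records that "Group B with 2.5 mg QD was selected as the maintenance dose".

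**Comparison and reporting.** Protocol 4.2, on avoiding bias, states that subjects will not be compared with one another or with historical controls. SAP 3.2 and 5.2 rule out statistical comparison of the regimens. Protocol 9.4 pools A and B for the primary and secondary efficacy analyses, and Protocol 9.4.1.3 adds summaries of ORR, DOR, CRR, PFS and OS by regimen.

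**The concern.** Choosing one of two regimens partly on their own data is a comparison, whether or not a test is run. Nothing in the design supports reading a difference between A and B as an effect of the maintenance schedule.

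If the IWRS alternates, fills one regimen before the other, or uses the baseline data entered, then regimen can be tied to enrolment period, site or patient type. In an open-label trial a predictable sequence also lets sites time enrolment. Case mix plausibly matters: Protocol 1.1 describes three clinically different MZL subtypes, and SAP 7.3.2 examines ORR by subtype, region, prior regimens and relapsed/refractory status. No adjustment for baseline differences between A and B is planned.

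The choice determines which regimen 30 more participants receive. It also closes the other regimen and lets its participants switch. In the final by-regimen tables, the 30 later participants all sit in the selected regimen, which adds a calendar-time difference.

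**Working it through.** **1. The plan's own figures concern the pooled cohort.** At n = 90, the smallest count with an exact 95% lower bound of at least 40% is 46, and P(X ≥ 46 | 90, 0.60) = 96.5%, against the stated 96%. At n = 60, 32 responders give an exact lower bound a hair under 40%. Counting that as 40% gives 88.2%, near the stated 90%; taken strictly, 33 are needed and the probability is 82.2%. The futility probabilities in SAP 10 reproduce as 0.291, 0.049 and 0.003 at true rates of 40%, 50% and 60%. None of these depends on how A and B were allocated. The documents give no operating characteristic for the regimen choice.

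**2. The passages side by side.**
- Protocol 4.1 and 5.1.1: a central system assigns A or B. No ratio, list, concealment or stratification is described.
- Protocol 5.1.2 and SAP 3.1: randomisation is stated not to apply, so this is a positive statement and not an omission.
- Synopsis, Protocol 4.1 and SAP 3: the resulting data help select a regimen.
- Protocol 4.2: subjects are not compared. This cannot stand beside the selection step.
- Protocol 1.4: planned dosing is identical for 8 weeks, and Protocol Table 6 puts the first scan at Week 8. An A–B difference in response at that scan would therefore largely reflect chance or case mix.

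**3. A hypothetical size.** Assumptions not in the documents: 30 per regimen, equal true ORR under both regimens, and selection of the regimen with more responders. The 60% is the Protocol 9.2 planning value. Let X_A ~ Bin(30, p_A) and X_B ~ Bin(30, p_B), with B taken arbitrarily as the favoured regimen.

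P(B looks better) = P(X_B > X_A) + ½ P(X_B = X_A)

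A 6-point shift arises if, for example, a subtype with a 30-point lower ORR is 20 points more common in A: 0.30 × 0.20 = 0.06. The 10-point shift is simply assumed.

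| Case-mix shift | p_A / p_B | P(X_B > X_A) | P(tie) | P(B looks better) |
|---|---|---|---|---|
| none | 0.60 / 0.60 | 0.448 | 0.105 | 0.448 + 0.052 = 0.50 |
| 6 points | 0.57 / 0.63 | 0.635 | 0.094 | 0.635 + 0.047 = 0.68 |
| 10 points | 0.55 / 0.65 | 0.747 | 0.077 | 0.747 + 0.038 = 0.79 |

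**4. Precision.** Even with random allocation, the 95% half-width for a difference in ORR is about 1.96 × √(2 × 0.6 × 0.4 / 30) = 24.8 points. Shifts of 6 or 10 points could not be told apart from chance in the observed data.

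**The case against.** The strongest reply is that no comparison of regimens is claimed. Efficacy is pooled, formal comparison is ruled out, and the choice also draws on safety and on other studies. Assignment is central and follows the eligibility check (Protocol 7.2), and nothing says that investigators pick the regimen. Protocol 5.1.1 refers to an IWRS Manual that may contain the rule. SAP 5.2 and 6.1 already tabulate baseline factors by regimen, so an imbalance would be visible. Randomising 30 per regimen would not guarantee balance either: for a factor present in 20% to 50% of participants (assumed), a chance imbalance of 20 points or more has probability of about 5% to 12% by normal approximation.

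Much of this stands. The pooled ORR is sound on this point, the data from this study are only part of the basis for the choice, and central assignment may prevent hand-picking. The figures above also assume equal true ORR, so they show a tilt in the choice and not a probability of choosing a worse regimen.

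The reply does not close the gap. Ruling out a test does not stop the data from informing the selection. With no rule stated, neither balance nor unpredictability can be assumed. The by-regimen baseline tables mix the later 30 into the selected regimen. Randomisation would remove systematic imbalance and leave only chance error, which can be quantified.

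**Conclusion.** The point holds as a limit on the regimen choice and on the by-regimen summaries. As written, both are open to confounding by case mix or calendar time, and Protocol 4.2 conflicts with the selection step. The 68% and 79% figures are hypothetical and rest on the assumptions in the working.

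A reader might infer more than the documents support:
- *That the selection of Treatment B was biased or wrong.* No A-versus-B results or baseline data are given, so confounding is possible but not shown.
- *That the primary ORR is compromised.* It pools both regimens and makes no A-versus-B contrast.
- *That allocation was certainly non-random, or chosen by investigators.* The documents say randomisation does not apply, but the IWRS rule is not described. If the system did randomise, the error lies in that statement.
- *That the SAP should now declare the first 60 randomised.* Selection was to follow completion of those 60, and the SAP records that it has taken place. Declaring random assignment now would misdescribe the trial unless it actually occurred.

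**What to change.** **Design text.** Protocol 5.1.2 and SAP 3.1 should have had the IWRS assign the first 60 Cohort 2 participants to A or B 1:1 at random, in concealed permuted blocks. Before enrolment this would have cost an IWRS setting and a sentence in each document, with no extra participants, visits or drug.

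**Current SAP, now that a regimen has been selected.**
1. In SAP 3.1, state the algorithm and ratio actually used. If allocation was in fact random, correct the not-applicable entries in both documents.
2. Otherwise, label all A-versus-B results as non-randomised.
3. Show baseline factors by regimen for the first 60, separately from the later 30.
4. Report A-versus-B response for the first 60 only.
5. Reconcile Protocol 4.2 with the regimen selection described in the synopsis and Protocol 4.1.

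The cost is a short paragraph and two restricted tables from data already collected.

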4.2. Measures Taken to Avoid Bias

This is an open-label study; no comparisons will be made between subjects or against historical controls. Measurements of safety and efficacy are objective measurements, and only comparisons to pretreatment conditions will be made. Safety will be objectively assessed using NCI CTCAE v4.03 (NCI 2010) guidelines and reviewed by the IDMC. Tumor response will be assessed by an IRC using the CT-based criteria of the Lugano classification (Cheson et al 2014).

4.3. Number of Subjects

4.3.1. Planned Number of Subjects

The study will enroll approximately 90 subjects at approximately 100 global investigative sites.

4.3.2. Replacement of Subjects

No subjects will be replaced at any time during this study.

4.4. Duration of Treatment and Subject Participation

After signing the ICF, screening assessments may be completed over a period of up to 28 days. Each subject enrolled in the study may continue to receive study treatment in continuous 28-day intervals. If the subject discontinues study treatment, the treatment period will end, and the subject will enter the 30 to 35-day safety follow-up period, after which the subject will enter the survival follow-up period (see Section 6.4.3). Subject participation is expected to average approximately 25 months.

4.5. Overall Study Duration

The study begins when the first subject signs the ICF. The end of the study will occur when **all** subjects have discontinued from the study (see Section 5.7) **or** have completed at least 24 months of study participation (starting from the first dose of study treatment). It is estimated that the study will take approximately 2 years to accrue approximately 90 subjects and that the final analysis will be performed no later than 2 years after the first dose of study treatment is administered to the last subject treated. Subjects who are still on study treatment and who have no evidence of progressive disease at the end of the study will have the option to continue on monotherapy with INCB050465 provided within a rollover Protocol, as local law permits (see Section 5.8).

4.6. Study Termination

The investigator retains the right to terminate study participation at any time, according to the terms specified in the study contract. The investigator is to notify the institutional review board (IRB)/independent ethics committee (IEC) in writing of the study's completion or early termination, send a copy of the notification to the sponsor or sponsor's designee, and retain 1 copy for the site study regulatory file.

The sponsor may terminate the study electively, if required by regulatory decision, or upon advice of the IDMC. If the study is terminated prematurely, the sponsor will notify the investigators, the IRBs and IECs, and regulatory bodies of the decision and reason for termination of the study. The IDMC will recommend termination of the study if warranted, as described in the IDMC Charter (see also Section 9.5).

